9.4.5 Periodical Reporting to Regulatory Authorities

Dompé shall be responsible to prepare and submit annual safety reports (Development Safety Update Report – DSUR) to relevant Regulatory Authorities in the countries concerned, as per applicable requirements.

9.5 EXPOSURE TO INVESTIGATIONAL PRODUCT DURING PREGNANCY

Women of childbearing potential are not excluded from the study as long as adequate birth control methods are being utilized. Women of childbearing potential are defined as all women physiologically capable of becoming pregnant. Adequate birth control methods are summarized in the protocol's exclusion criteria.

Prior to enrollment in the clinical trial, female patients of childbearing potential and their partners must be advised of the importance of avoiding pregnancy during the entire course of the study treatment and for the 30 days after the study treatment period ends and of the potential risks associated with an unintentional pregnancy. During the trial (during the study treatment period and during the follow-up), female patients are to be instructed to contact the Investigator immediately if they suspect they might be pregnant; in the same way, male patients who become aware that the partner might be pregnant, are to be instructed to contact the Investigator immediately.

The Investigator must report every pregnancy on a pregnancy report form as soon as possible (within 24 hours of learning of the pregnancy) to CRO/Dompé Pharmacovigilance, Safety and Surveillance contacts reported at § 9.4.1, even if no AE has occurred, and follow it to term.

The pregnancy form will be utilized to capture all pregnancy-related information until the birth of the child for both the patient and the partner.

If the pregnancy is associated with a SAE (e.g., if the mother is hospitalized for dehydration), in addition to the pregnancy report form, a separate SAE report form must be filed as described in § 9.4 with the appropriate serious criterion (e.g., hospitalization) indicated on the SAE report form. Miscarriage, stillbirth, and any malformation/disease must be reported as a SAE. Any pregnancy leads to the immediate cessation of the study treatment.

9.6 ADVERSE EVENTS CAUSING TREATMENT DISCONTINUATION

If a patient is withdrawn from the study as a consequence of an AE, this must be recorded and reasoned in the eCRF, and the patient must be followed up until the resolution of the AE or as instructed by the medical monitor.

9.7 OVERDOSE

Overdose (accidental or intentional) of Study Products (including vehicle) which may or may not result in serious adverse reactions, shall be reported to Sponsor Global Pharmacovigilance, Safety and Surveillance /CRO by email or fax, following the same procedure for SAE, within 24 hours from the Investigator's knowledge of its occurrence. This includes reports related to intake through different routes (e.g., ingestion) or with suicidal intentions and consequent drug overdose.

Since in the preclinical toxicology studies in animals and in the multiple ascending dose study

performed in healthy volunteers none of the dose has caused an overdose as documented by adverse reaction, for the purpose of this study we define that the administration of more than 3 times the total daily dose on any given treatment day will be reported as an overdose, even if not associated with adverse reactions. The Investigator shall provide in the SAE form information about symptoms, corrective treatment, and outcome of overdose.

The Medical Expert should be contacted to discuss corrective treatment, if necessary.

10 STATISTICS

10.1 SAMPLE SIZE

The sample size of the study is calculated based on results from the previous study NGF0118 using the subgroup of patients with baseline SANDE Global Score > 50. Expecting a mean difference of about 11 points (with unequal standard deviations in the active and vehicle groups: observed mean changes (SD) were -28.2 (26.36) and -17.4 (20.29) for IMP and vehicle, respectively) in improvement of SANDE Global Score from baseline to Week 8 in favor of rhNGF ophthalmic (eye drop) formulation, a total sample size of 276 evaluable patients (92 per group) is needed. This will allow to achieve an overall power of 80% for demonstrating superiority of at least one concentration of rhNGF ophthalmic formulation over vehicle in the improvement of SANDE Global Score from baseline to week 8, with an overall one-sided alpha of 0.025.

The sample size calculation takes into consideration a Bonferroni correction for two comparisons (2 concentration groups versus vehicle), i.e., the alpha level has been set to 0.0125 one-sided for each comparison.

Assuming a 5% rate of patients not evaluable for primary analysis after enrollment, the total number of patients to be enrolled in the study will be about 291 (97 per group). Enrollment will be competitive.

In Dompé previous studies, a screen failure rate of about 20% has been observed (NGF0121 - PROTEGO-1). This fact implies that approximately 350 subjects will need to be screened in order to have 291 patients enrolled and at least 276 evaluable. In any case, the screen procedures should be interrupted when the expected sample size of 291 subjects has been reached.

10.2 OVERVIEW OF PLANNED STATISTICAL ANALYSIS

The study plans only a final analysis: this analysis will be conducted when all randomized subjects have completed the study [treatment at week 4 (V4) and follow-up at week 8 (V5)] and the study database has been locked and unmasked.

10.3 INTERIM ANALYSIS

No interim analyses are foreseen.

10.4 PATIENT POPULATION

10.4.1 Screened Population (SCR)

A patient will be defined as screened after the signature of the informed consent, the assignment of a Screening number and regardless of the completion of all the screening procedures. eCRF should be completed for each patient that signed the informed consent, including the screening failures.

10.4.2 Enrolled Population (ENR)

A patient in the SCR population will be defined as enrolled if meets all the inclusion criteria and no one of the exclusion criteria at the end of the screening procedure at Visit 1 (Day - 12±2) and Visit 2 (Day 1). Patients in the SCR population but not included in the ENR population will be defined as screen failures.

10.4.3 Randomized Population (RND)

The Randomized Population will consist of all patients in the ENR Population who were assigned a randomization number.

10.4.4 Safety Population (SAF)

The Safety (SAF) population will consist of all Patients in the RND population who received at least one dose of the IMP. Safety population will be analyzed according to the actual treatment received. The SAF population will be used to present results on safety data.

10.4.5 Full Analysis Set (FAS)

The Full Analysis Set (FAS) will consist of all Participants in the RND Population who took at least one dose of IMP. The FAS will be analyzed according to the intention-to-treat (ITT) principle, i.e., by treatment allocation. The FAS population will be used for the primary analysis of the study and to present results on efficacy data.

10.4.6 Per Protocol Population (PP)

The Per Protocol (PP) Population will consist of all patients in the FAS population who do not have major protocol deviations. Primary efficacy analysis will be conducted on the FAS population while SAF and PP populations will be used for safety and sensitivity analysis, respectively.

Reasons for the exclusion from the PP population will be determined in the masked Data Review Meeting (DRM). A non-exhaustive list of possible reasons for exclusion from the PP can be the following:

- Lack of compliance with IMP and NIMP administration. (§1.1, §4.1, §9.7, §11.6)
- Missing of any efficacy data post randomization.
- Intake of prohibited medications. (§4.1, §6.6.1)

10.5 ESTIMANDS

The estimands for the primary and key secondary objectives are defined in §s [3.2.1](#) and [3.2.2](#), respectively.

10.6 STATISTICAL METHODOLOGY

Statistical analysis will be performed by the CRO appointed by Dompé.

10.6.1 Descriptive Statistics

Appropriate descriptive statistics will be produced by treatment arms according to the nature of the variable. For continuous data, the number of observations, mean, standard deviation, median (25th and 75th percentile) and range (minimum and maximum) will be presented. For qualitative data, frequency distributions and percentages per category will be presented. If appropriate, confidence intervals around the mean or the proportion will be presented. The number of subjects with missing data will be presented under the “Missing” category. Missing values will not be included in the denominator count when computing percentages. When continuous data will be summarized, only the non-missing values will be evaluated for computing summary statistics. Any exception will be declared.

For the purpose of efficacy analysis in this trial, the statistical analysis (both descriptive and inferential) will be done on the Study Eye. Details will be provided in the statistical analysis outputs as notes. In case analysis involves both eyes, it will be clearly declared.

The significance level used for primary analysis will be 0.0125 one-sided for each active arm versus vehicle and will be determined in accordance with the Hochberg approach ([Hochberg Y. 1988](#)) for the key secondary endpoints (in order to preserve an overall 0.025 one-sided). Unless otherwise specified, the significance level used for other statistical testing will be 0.05 and two-sided tests will be used. All patient data collected on the eCRF will be listed by patient and center.

Data transformation (e.g., log transformation) might be used in order to satisfy the assumption of normality requested by parametric statistical tests and models. In case such assumptions are not met even on the transformed data, non-parametric counterpart tests will be used. In case of log transformation, also a back transformation of the results will be provided in order to facilitate the clinical interpretation.

The Statistical Analysis Plan (SAP) will be issued before database lock with more technical and detailed elaboration of the principal features of statistical analyses. Additional post-hoc analysis may be produced to further allow comparison between treatment and control, according to the results obtained. Any deviation from the original statistical plan (including unplanned analyses) will be documented in the Clinical Study Report.

10.6.2 Primary Analysis of Efficacy Variables

The overall null hypothesis H_0 is that the change from baseline in the SANDE Global Score for at least one of the two concentrations of rhNGF ophthalmic solution (CCI and CCI) is greater or equal (worse and no improvement, respectively) than the vehicle one (μ_{VEHICLE}):

$$H_0: \text{CCI} \geq \mu_{\text{VEHICLE}} \text{ AND } \text{CCI} \geq \mu_{\text{VEHICLE}}$$

$$H_1: \text{CCI} < \mu_{\text{VEHICLE}} \text{ OR } \text{CCI} < \mu_{\text{VEHICLE}}$$

where for SANDE Global Scale lower score is better.

Considering the multiple comparisons (each concentration group versus vehicle) to claim superiority, a Bonferroni multiplicity correction of type I error will be applied on primary endpoint comparison. Each concentration group will be consequently tested at one-sided $\alpha = 0.0125$, in order to preserve the overall one-sided α of 0.025. The null hypothesis H_0 will be rejected if the associated primary analysis one-sided p-value will be lower than 0.0125 for at least one of the two concentration groups versus vehicle.

The primary endpoint (i.e., the change from baseline in SANDE global score at week 8) will be analyzed by means of a mixed model for repeated measures (MMRM) in the FAS. The analyses will include the fixed effects of treatment (3 levels: rhNGF C mcg/mL, rhNGF C mcg/mL and vehicle), visit (2 levels: Weeks 4, 8), baseline value, and treatment by visit interaction. The covariance matrix used will be "unstructured". Each concentration group (IMP1 and IMP2) will be compared with the vehicle group at Week 8 using the least square mean differences (i.e., the mean difference between each concentration group and vehicle over time). The model can be summarized as follows:

change from baseline

$$= \beta_0 + \beta_1 \text{treatment} + \beta_2 \text{base} + \beta_3 \text{visit} + \beta_4 \text{treatment} * \text{visit} + \varepsilon$$

where $\varepsilon \sim N(0, R)$ and R is the unstructured covariance matrix with blocks defined by the subjects. Further details and SAS code will be described in the SAP that will be generated before the DB lock and the unmasking.

For patients analyzed under the hypothetical strategy (see § 3.2.1), any data collected in the week after the ICE of interest (intake of prohibited medications) will be considered as missing for the purpose of the primary analysis and will be imputed, as well as the other missing data (for example for lost to follow-up, patients who withdrew their consent), by using the multiple imputation described below with a copy-reference approach.

Missing data that may be obtained notwithstanding the intent to apply the treatment policy strategy and after having applied the hypothetical strategy when needed, will be addressed by using multiple imputation (MI) based on copy-reference approach. This approach does not assume benefits for the rhNGF in case of discontinuation and limits a post-discontinuation clinical effect to that of the vehicle. Specifically, the copy-reference approach will be implemented in this way:

- 1) Intermittent and monotone missing data for SANDE Global Score at baseline, Week 4 and Week 8 will be imputed by using the Fully Conditional Specification (FCS) method under the missing not at random (MNAR) assumption where only the subset

of observations that come from the Vehicle group are used to derive the imputation model.

- 2) For each imputed dataset, the change from baseline at Week 4 and Week 8 is derived.
- 3) The change from baseline at Week 4 and Week 8 will then be used in a MMRM as described above with change from baseline as dependent variable and baseline value, treatment arm, visit and treatment by visit interaction as independent variable. Subject will be considered as cluster variable and an unstructured covariance matrix will be set to model the within-subject correlation.
- 4) Results obtained on each imputed dataset will be combined using Rubin's rule to draw inference.

The adjusted estimated treatment difference between each concentration of the rhNGF new formulation and vehicle will be displayed together with the corresponding two-sided 95% confidence interval (CI) and one-sided p-value.

In case both concentrations of rhNGF differ from placebo, the choice between the two concentrations will be based on the size of the effect (and corresponding CI), on the results of secondary endpoints and on safety data.

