3.2 PRIMARY AND KEY SECONDARY ESTIMANDS

3.2.1 Primary Estimand

The estimand for the primary objective is defined as follows:

- Treatment: 4 weeks follow up after 4 weeks of TID administration of rhNGF new formulation (two concentrations and vehicle).
- Population: Male and female patients aged ≥ 18 years with dry eye. Full Analysis Set.
- Variable: mean change from baseline to week 8 in symptoms of dry eye assessed by SANDE Global Score.
- Intercurrent events (ICEs) and strategies to handle them:
 - Treatment discontinuation: a treatment policy strategy will be applied where all the observed values will be used regardless of the occurrence of the ICEs. Missing data due to any reason will be handled by using a multiple imputation with a copy-reference approach (see § 10.6.2 for further details).
 - Use of a prohibited medication, as listed in § 6.6.1, in the week before any assessment of SANDE Global Score: a hypothetical strategy will be applied where any data collected in the week after the occurrence of the ICE will be discarded. Missing data will be imputed by using a multiple imputation with copy-reference approach (see § 10.6.2 for further details).
- Population-level summary: difference in mean change from baseline to week 8 in symptoms of dry eye assessed by SANDE Global Score between each concentration group of IMP (groups IMP1 and IMP2) and the vehicle group as derived by the Mixed Model for repeated measures defined in § 10.6.2.

In summary, the primary estimand is defined as the difference in mean change from baseline to week 8 in symptoms of dry eye assessed by SANDE Global Score between treatments in the targeted patient population regardless of study treatment discontinuation and had prohibited medications not been available to subjects in the week before any study evaluation.

More details are provided in the statistical § 10.

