 - Treatment discontinuation: a treatment policy strategy will be applied where all the observed values will be used regardless of the occurrence of the ICEs. Missing data due to any reason will be handled by using a multiple imputation with a copy-reference approach (see § 10.6.2 for further details).
 - Use of a prohibited medication listed in § 6.6.1 at any time during the study: a hypothetical strategy will be applied where any data collected after the first administration of a prohibited medication will be discarded. Missing data will be imputed by using a multiple imputation with copy-reference approach (see § 10.6.2 for further details).
- Modified strategy #2 to handle ICEs for primary estimand:
 - Treatment discontinuation: a treatment policy strategy will be applied where all the observed values will be used regardless of the occurrence of the ICEs. Missing data due to any reason will be handled by using a multiple imputation with a copy-reference approach (see § 10.6.2 for further details).
 - Use of a prohibited medication listed in § 6.6.1 in the week before any assessment of SANDE: a composite strategy will be applied where any data collected in the week after the occurrence of the ICE (if present) will be replaced by a value worse than all values observed for SANDE at week 8.

The modified estimand #1 will be analysed as described for the primary estimand.

For the modified estimand #2, the trimmed approach by Permutt and Li ([Permutt T and Feng L. 2017](#)) will be used. This method provides an exact test that does not require any modeling assumption. The estimand of the primary analysis is the difference between treatment groups in mean SANDE change from baseline to week 8 in the FAS population, including all patients who have no SANDE measurement at week 8 for any reason. The exact imputed value does not matter, as long as it is worse than all values observed in patients with SANDE measurements at week 8. The only requirement for this method is that it must be reasonable to consider the outcome of dropouts as worse than the highest SANDE Global Score of the completers.

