4.4.1. Baseline

For the purpose of the statistical analysis, Baseline is defined as the last visit prior to and including date of the randomization visit (V2 – Day 1). Unless otherwise specified, baseline values are defined as the measurements taken during this visit. In case of multiple measurements

during baseline visit, the last assessment will be considered as the baseline evaluation. In case of missing value at baseline visit, but availability of other values collected before the first administration of the IMP (e.g. at Screening), the last available value collected will be used as the baseline value.

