13.3. SAS Code for Primary Analysis

Step 1: Multiple Imputation

```
PROC SORT data=efficacy;  
  by USUBJID;  
RUN;
```

```
PROC MI data=efficacy nimpute=50 out=mi_data min=0 max=100 seed= 47292748; *score range: 0-100;  
  class TRTPN;  
  var V2 V4 V5; *V2=baseline, V4=Week 4, V5=Week 8;  
  FCS regression;  
  mnar model(V2 V4 V5/ modelobs=(TRTPN='3')); *Vehicle group has TRTPN=3;  
RUN;
```

Data will be transformed to short format by AVISITN before applying multiple imputation.
The MI method will be used for both primary and secondary analyses after applying appropriate ICE handling strategies.

Step 2: MMRM Model

```
PROC MIXED data= mi_data_long;  
  by _imputation;  
  class TRTPN AVISITN USUBJID;  
  model CHG=BASE TRTPN AVISITN TRTPN*AVISITN / DDFM=KR CL;  
  repeated AVISITN/subject=USUBJID type=UN;  
  lsmeans TRTPN*AVISITN/diff cl;  
  ods output lsmeans=lsM diffs=diffM;  
RUN;
```

Data will be transformed back to long format by combining visits before applying MMRM model.
If model fails to converge, the “type=UN” will be replaced by “type=CS”.
This model is the essential model for primary endpoint. Appropriate adjustments may be made based on modified Estimand strategies and sensitivity analyses.

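### The prohibited-medication rule can discard the Visit 2 baseline SANDE, and the primary imputation would then rebuild it from the patient's own Week 4 and Week 8 scores; the SAP does not say whether its baseline fallback prevents this

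*Protocol*

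**What the plan says.** The primary estimand (protocol 3.2.1; SAP 3.3.1) names as an intercurrent event "Use of a prohibited medication, as listed in § 6.6.1, in the week before any assessment of SANDE Global Score" and handles it by a hypothetical strategy: values collected in the following week are dropped and imputed. SAP 13.4 classifies use as prohibited when the medication stops after the consent date, so use during the run-in counts.

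Protocol 10.6.2 then specifies: "Intermittent and monotone missing data for SANDE Global Score at baseline, Week 4 and Week 8 will be imputed". The method is fully conditional specification with a model derived from vehicle patients only. SAP 8.1.1 repeats this, and the code in SAP 13.3 has "mnar model(V2 V4 V5/ modelobs=(TRTPN='3", where V2 is baseline, V4 is Week 4 and V5 is Week 8. Imputed values are bounded at 0 and 100. The change scores are computed after imputation, and baseline is also a covariate in the MMRM.

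SAP 4.4.1 provides that when the baseline-visit value is missing and another pre-dose value exists, for example from Screening, "the last available value collected will be used as the baseline value". SANDE is collected at Screening. SAP section 1 makes the SAP govern where the two documents disagree.

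**The concern.** Baseline SANDE is measured before randomisation, so treatment cannot affect it. Even if run-in medication influenced it, adjusting for the observed value leaves the comparison between arms valid. Replacing it with a prediction from Week 4 and Week 8 removes that property. On a working dose those later scores contain the drug effect, but the vehicle-only model reads a low later score as a sign of a low starting score. The imputed rhNGF baseline then tends to be too low, and adjusting for it takes away part of the effect. The imputed value can also fall below 50, the entry limit that the observed score had to meet.

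The key secondary endpoints use the same discard rule and imputation strategy with only baseline and Week 4 data (protocol 10.6.4). A discarded Schirmer-I or corneal staining baseline would therefore be predicted from the endpoint visit itself.

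**Working it through.** **The plan's own figure.** Protocol 10.1 gives "observed mean changes (SD) were -28.2 (26.36) and -17.4 (20.29) for IMP and vehicle, respectively", so the difference is 28.2 − 17.4 = 10.8. It adds that "the alpha level has been set to 0.0125 one-sided for each comparison", with the aim to "achieve an overall power of 80" percent. A two-sample calculation with unequal variances (Welch, noncentral t) gives 92 per group with power 0.802; the normal approximation gives 91. Then 92/0.95 = 96.8, rounded up to 97, and 3 × 97 = 291. The stated sample size reproduces.

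**Can baseline be missing at imputation?** SANDE is an entry criterion assessed at Visits 1 and 2, so a randomised patient has a pre-dose value. A baseline becomes missing in practice only by being discarded. If the 4.4.1 fallback always covered that case, V2 would almost never need imputing, and naming it as a target would serve no purpose. The nearest stated order is in SAP 4.4, which fills missing visits from other visits before any intercurrent-event handling. If the baseline fallback follows the same order, it comes too early to rescue a discarded value. No text settles this.

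**Size where baseline is imputed.** With Week 4 and Week 8 observed:

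- shift in imputed rhNGF baseline = b4·d4 + b8·d8
- loss of adjusted Week 8 effect = share discarded × slope of Week 8 on baseline × size of that shift

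Here b4 and b8 are the vehicle regression coefficients of baseline on Weeks 4 and 8, and d4 and d8 are the drug effects. From the documents: d8 = −10.8 and vehicle SD of change 20.29. Assumed, because the documents do not give them: baseline SD 12, the between-visit correlations, d4, and the share discarded.

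Example with equal correlation 0.5. The later-visit SD s solves 12² + s² − 2(0.5)(12)s = 20.29², so s = 23.4. Then b4 = b8 = (0.5/1.5)(12/23.4) = 0.171. With d4 = −5.4 the shift is 0.171 × (−16.2) = −2.77. The slope is 0.5 × 23.4/12 = 0.98, so the loss is 2.70 points per affected patient, or 0.27 points at 10% discarded.

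| Correlation pattern | d4 | Baseline shift | Loss at 5% | 10% | 20% |
|---|---|---|---|---|---|
| equal, 0.3 | −5.4 | −2.20 | 0.06 | 0.11 | 0.22 |
| equal, 0.5 | −5.4 | −2.77 | 0.13 | 0.27 | 0.54 |
| equal, 0.7 | −5.4 | −2.99 | 0.23 | 0.47 | 0.93 |
| equal, 0.5 | 0 | −1.84 | 0.09 | 0.18 | 0.36 |
| equal, 0.5 | +5 | −0.99 | 0.05 | 0.10 | 0.19 |
| decaying (AR(1)), 0.7 | −5.4 | −1.95 | 0.09 | 0.19 | 0.37 |
| decaying (AR(1)), 0.7 | 0 | 0 | 0 | 0 | 0 |
| decaying (AR(1)), 0.7 | +5 | +1.81 | −0.09 | −0.17 | −0.34 |

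A negative loss favours the drug. With equal correlations of 0.3 to 0.7 and d4 anywhere from 0 to −10.8, the loss at 10% discarded runs from 0.07 to 0.62. The upper end rests on correlation 0.7, which implies a steep slope of 1.56.

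**Simulation.** 92 per arm, Bayesian regression imputation of baseline from vehicle patients, ANCOVA at Week 8 standing in for the MMRM, Rubin's rules with 20 imputations, 1,500 runs. With equal correlation 0.5 and d4 = −5.4, power with observed versus imputed baselines was 0.809 and 0.801 (5% discarded), 0.817 and 0.793 (10%), and 0.795 and 0.750 (20%). The worst setting run (correlation 0.7, 20%) gave 0.819 and 0.733. With no treatment effect (3,000 runs, 20% discarded), one-sided rejection was 0.015 with observed and 0.012 with imputed baselines, against a nominal 0.0125.

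**The case against.** The strongest reply is that SAP 4.4.1 already solves the problem. It defines baseline for analysis, the SAP governs, and a Screening SANDE exists for every randomised patient. If the fallback covers a discarded Visit 2 value, V2 is complete, naming it in the MNAR statement does nothing, and no leak arises. This makes the defect conditional. It does not remove it, because nothing extends the fallback to discarded values, and listing baseline as an imputation target suggests otherwise.

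Second, the direction is not fixed. Protocol 4.2 reports that in the earlier dry eye trial SANDE improved significantly in follow-up but not during treatment, and eye pain on treatment was common (protocol 6.2). A null or adverse Week 4 effect is therefore plausible, and the table shows a zero or reversed leak in such cases when correlation decays over time. This stands.

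Third, few baselines may be affected: only the sponsor's vehicle is allowed in the run-in, and medications and diary are reviewed at Visit 2 before randomisation. This is fair, though the documents give no share. The planned all-observed-cases analysis would also restore discarded values, but it is not the primary analysis, and protocol 10.6.3 ties the sensitivity analyses to a significant primary result.

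A reader might also take modified strategy #1 as evidence of the leak, since there "any data collected after the first administration of a prohibited medication will be discarded". It is not: run-in use that removes V2 under that strategy also removes V4 and V5, so the patient's own later scores are not available to predict the baseline.

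**Conclusion.** The point holds in conditional form. Read literally, the discard rule and the imputation step together can replace an observed pre-randomisation SANDE with a function of the outcome, and the SAP does not reconcile this with its own baseline fallback.

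The effect is small. If 10% of baselines are discarded, a true 10.8-point effect loses about 0.1 to 0.5 points with equal correlations of 0.3 to 0.7 and half the effect present at Week 4. The share, baseline SD, correlations and Week 4 effect are all assumptions.

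A reader might infer that the plan certainly imputes discarded baselines, that it always shrinks the effect, or that it threatens type I error. The documents support none of these: the fallback may apply, the leak can be zero or reverse, and with no treatment effect there is no bias.

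For the key secondary endpoints the mechanism is the same, and a null Week 4 effect is no safeguard because Week 4 is the endpoint. The size there was not computed.

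**What to change.** In protocol 3.2 and 10.6.2 and SAP 3.3, 8.1.1, 8.2.1 and 13.3:

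- Limit the prohibited-medication intercurrent event to assessments after randomisation.
- Keep the observed Visit 2 value as baseline, and use the SAP 4.4.1 fallback only when Visit 2 was not collected.
- Remove V2 from the `MNAR MODEL` list, keeping it in the imputation as a predictor of V4 and V5.
- Make the same changes for Schirmer-I and corneal staining.

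The cost is a few sentences and one line of code, settled before unmasking. No new data are needed and the sample size does not change.
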